#### **6.1.2 Data Collection/Recording Exceptions**

##### **6.1.2.1 Abnormal Laboratory Values**

An abnormal laboratory value will be recorded as an AE **only** if the laboratory abnormality is characterized by any of the following:

- Results in discontinuation from the study
- Is associated with clinical signs or symptoms

- Requires treatment or any other therapeutic intervention
- Is associated with death or another serious adverse event, including hospitalization.
- Is judged by the Investigator to be of significant clinical impact
- If any abnormal laboratory result is considered clinically significant, the investigator will provide details about the action taken with respect to the test drug and about the patient's outcome.

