**Figure 3: Arm 1: FL Dose-finding**

**Figure 4: Arm 2: MZL, MCL and CLL Dose-finding**

**Figure 5: Arms 3 and 4 – Dose Expansion**

### 3.1.4 Dose-Limiting Toxicity

Dose limiting toxicities (DLTs) will be assessed during the venetoclax dose-finding for Arms 1 and 2 as follows:

- the first 4 weeks of triplet combination therapy for patients enrolled in Arm 1, Cohort 1 (C1D1 to C1D28)

- the first 5 weeks after starting venetoclax in Arm 2, Cohort 2 (C1D1 to C1D35).

Dose reductions of magrolimab and obinutuzumab are not permitted during DLT assessment period.

A DLT for this study is defined as any grade 3 or higher adverse event that is clinically relevant and deemed probably or definitely related to any of the study drugs or to the combination therapy, in the opinion of the Principal Investigator and occurs during the venetoclax dose-finding period with the exception of following:

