#### 3.1.4.2 Hematologic AEs

- Grade 3 neutropenia not associated with clinical sequelae
- Grade 3 thrombocytopenia not associated with  $\geq$  grade 2 bleeding
- Grade 3 anemia that lasts less than 3 days and responds to blood transfusion. **NOTE:** Grade 3 hemolytic anemia that requires hospitalization or prolongation of existing hospitalization, is disabling, or limits self-care activities of daily life (ADLs) will be considered a DLT.
- Grade 3 or 4 lymphopenia

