### 3.2.1 Magrolimab Administration

All patients will receive a magrolimab priming dose of 1 mg/kg on Day 2 of the first cycle of treatment. The duration of infusion of the priming dose will be 3 hours ( $\pm 30$  minutes). Use of an inline filter is required. All subsequent loading or maintenance doses of magrolimab will be infused over a duration of 2 hours ( $\pm 10$  minutes). When both obinutuzumab and magrolimab are given on the same visit day, obinutuzumab will be administered at least 1 hour after the completion of

magrolimab administration. All patients should be monitored for 1 hour post-infusion for all doses during Cycle -2. Post-infusion monitoring should begin after the last study drug is given. Post-infusion monitoring is not required for doses after Cycle 1, Day 22 for Arms 1 and 2 (dose-finding arms), and Cycle -2, Day 22 for Arms 3 and 4 (dose expansion arms). Patients who experience any treatment-related AEs during the observation period should be further monitored, as clinically appropriate.

Complete Blood Count with Differential will be performed prior to each dose, and 3-6 hours after the first and second doses of magrolimab - Cycle 1, Days 2 and 8 for dose-finding arms (Arms 1 and 2), and Cycle -2, Days 2 and 8 for dose-escalation arms (Arms 3 and 4). Complete Blood Count with Differential will also be performed twice weekly for the first cycle (Cycle 1 for dose-finding arms [Arms 1 and 2], and Cycle -2 for dose-escalation arms [Arms 3 and 4]).

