### **10.4.4 Safety Analyses**

The type, grade and frequency of toxicities will be reported. DLTs, MTD of venetoclax in combination with magrolimab and obinutuzumab; and SAEs will be reported as well.

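### Laboratory values become adverse events without reference to CTCAE grade, so asymptomatic, untreated Grade 3-4 cytopenias can be missing from the toxicity tables and, at Grade 4 only, from DLT review

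*Combined protocol and SAP*

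**What the plan says.** Section 6.1.2.1 makes an abnormal laboratory value an AE only "if the laboratory abnormality is characterized by any of the following". The triggers are:

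- "Results in discontinuation from the study"
- association with clinical signs or symptoms
- "Requires treatment or any other therapeutic intervention"
- association with death or another serious event, including hospitalization
- "Is judged by the Investigator to be of significant clinical impact"

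Section 10.4.4 then states: "The type, grade and frequency of toxicities will be reported". Section 10.4.2 analyses the primary endpoint as the type, number and frequency of DLTs. Section 3.1.4 builds the DLT on "any grade 3 or higher adverse event that is clinically relevant and deemed probably or definitely related" to study treatment, in the Principal Investigator's opinion, and then lists exceptions. One of these, in Section 3.1.4.2, is "Grade 3 neutropenia not associated with clinical sequelae".

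Two other sections bear on the point. Section 8.1.1 counts an abnormal laboratory finding among possible AEs without any such filter. Table 16 in Section 3.3.2 acts on the CTCAE grade of neutropenia, thrombocytopenia and anemia, including Grade 3 or 4 neutropenia with no fever or infection.

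**The concern.** Safety is the primary objective, and cytopenias are central among the expected toxicities. The protocol's own background tables give Grade 3/4 neutropenia of 53% with venetoclax-obinutuzumab (Table 6) and 41% with venetoclax alone (Table 1).

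Under Section 6.1.2.1, whether a low count becomes an AE depends on what the physician does and thinks about it. Growth factors and transfusion are left to investigator discretion (Section 3.3.2). The same neutrophil count is an AE in a patient given G-CSF and need not be one in a patient who is observed. The recorded frequency would then partly measure practice rather than toxicity.

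The DLT count is also exposed at one point. The definition starts from an adverse event, so a count never recorded as one has no clear route into DLT review. Two DLTs in six patients lead to the lower venetoclax dose level (Table 8), so a single missed event can matter.

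**Working it through.** **1. What the recording rule changes, by event.** Take a cytopenia that is asymptomatic and untreated, has no linked SAE or discontinuation from the study, and is not judged important. It meets no trigger in Section 6.1.2.1. The consequence for the DLT count differs by type and grade:

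| Event | Excepted in 3.1.4.2? | What 6.1.2.1 can remove |
|---|---|---|
| Grade 3 neutropenia, no sequelae | Yes | Toxicity-table entry only |
| Grade 3 thrombocytopenia, no bleeding of grade 2 or more | Yes | Toxicity-table entry only |
| Grade 3 or 4 lymphopenia | Yes, both grades | Toxicity-table entry only |
| Grade 4 neutropenia or thrombocytopenia | No | Toxicity-table entry and a potential DLT |

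Anemia adds little. Short, transfusion-responsive Grade 3 anemia is excepted, and longer anemia is not, but a transfusion is a treatment and so makes the value recordable.

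**2. Recording rule against the dose-modification rule.** In the window, and in triplet therapy after the DLT assessment, Table 16 requires infusions to be delayed for Grade 3 or 4 neutropenia even without fever or infection. In triplet therapy it also holds venetoclax and allows restart one level lower. Section 6.1.2.1 does not name a hold, delay or reduction. Whether a hold counts as a therapeutic intervention is not defined. An event that interrupts all study drugs can therefore lack a clear AE record.

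**3. Size of the loss in the toxicity tables.** The plan gives no figure to reproduce. The background rates are 112/212 = 53% and 48/116 = 41%. Both pool Grades 3 and 4, and neither is split by symptoms or treatment. They cannot size the loss, and no estimate is offered.

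**4. Illustration for the DLT rule.** All rates here are assumptions. Let *a* be the DLT rate from other causes, *g* the independent rate of asymptomatic, untreated Grade 4 neutropenia or thrombocytopenia, and *r* the share of these that is counted. For six evaluable patients:

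p = 1 − (1 − a)(1 − r·g)

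P(at least 2 of 6) = 1 − (1 − p)^6 − 6p(1 − p)^5

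With a = 0.10 and g = 0.10:

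- r = 1: p = 1 − 0.90 × 0.90 = 0.19, and 1 − 0.2824 − 0.3975 = 0.320
- r = 0.5: p = 1 − 0.90 × 0.95 = 0.145, giving 0.212
- r = 0: p = 0.10, and 1 − 0.5314 − 0.3543 = 0.114

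Over a wider range:

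| a | g = 5%, all counted | g = 10%, all counted | g = 20%, all counted | none counted |
|---|---|---|---|---|
| 5% | 0.109 | 0.212 | 0.442 | 0.033 |
| 10% | 0.212 | 0.320 | 0.536 | 0.114 |
| 20% | 0.442 | 0.536 | 0.699 | 0.345 |

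These differences are upper limits. The all-counted columns assume that every such event would also be held clinically relevant and probably or definitely related.

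**5. Whether the data exist.** Section 3.2.1 schedules a CBC before each magrolimab dose and adds: "Complete Blood Count with Differential will also be performed twice weekly for the first cycle". For Arms 1 and 2 that cycle is the DLT window. Appendix G schedules CBC and chemistry at each cycle. Grades can therefore be derived without new procedures.

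**The case against.** The strongest reply is that few events would be lost. A Grade 4 count answered with G-CSF or transfusion is recorded as treated, and Section 3.4.2.4 strongly encourages G-CSF prophylaxis in patients at high risk. An investigator may well judge a Grade 4 count important. The DLT definition also has its own clinical-relevance test. A count judged to lack significant impact would probably fail that test too, so recording it might not change the DLT count. This stands, and it is why the DLT part is confined to Grade 4 and the figures above are upper limits.

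Second, Section 10.4.4 does not say that toxicities come only from recorded AEs, and Section 8.1.1 has a broad AE definition. That is also true. But Section 10.4 names no other source, and the specific recording rule in 6.1.2.1 is narrower than the general definition. The plan is at best silent.

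Third, the toxicity tables are not the primary analysis, since Section 10.4.2 names DLTs. The tables still support the primary safety objective.

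None of this answers the point that grade and dose interruption are missing from the recording triggers.

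**Conclusion.** The point holds for the toxicity tables: asymptomatic, untreated Grade 3-4 cytopenias can be absent, including ones that Table 16 acts on, and how many are absent depends on investigator judgement and supportive-care practice. The size is unknown from the documents. For DLTs it holds only for Grade 4 neutropenia or thrombocytopenia that is asymptomatic, untreated and not judged important. The possible effect on the 2-of-6 rule depends on assumed rates and on the clinical-relevance test. This is a reporting improvement worth making, not a defect that invalidates the design.

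Three stronger readings are tempting but not supported:

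- A reader might infer that asymptomatic Grade 3 cytopenias are also lost from the DLT count. For neutropenia and thrombocytopenia, and for lymphopenia of either grade, Section 3.1.4.2 excludes them deliberately, so the recording rule changes nothing.
- A reader might infer that recorded rates here could not be compared with the cited 53%. That figure comes from an AE summary table, and the cited trial's recording rule is not in the documents.
- A reader might scale the 53% by an assumed asymptomatic share to state an under-count. Nothing in the documents anchors such a share. The figure also comes from previously untreated CLL, whereas this trial enrols relapsed or refractory disease of four histologies.

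**What to change.** Add to Section 10.4.4 that scheduled hematology and chemistry results will be graded by CTCAE version 5 from the laboratory data, whether or not they were recorded as AEs. Report worst-grade and baseline-to-worst shift tables by arm beside the recorded AEs. Because the twice-weekly counts fall in Cycle 1 for Arms 1 and 2 but in Cycle -2 for Arms 3 and 4, the tables should state the period covered.

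Reconcile Section 6.1.2.1 with Sections 3.1.4, 3.1.4.2 and 8.1.1 and with Table 16. The text should make clear whether a hold or delay makes a laboratory value an AE. It should also make clear whether Grade 4 cytopenias in the DLT window are brought to DLT review when not recorded as AEs. Which way that is settled is for the sponsor and investigators. Letting laboratory grade alone decide a DLT would change the dose-decision rule and is not proposed here.

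The cost is a few programmed tables from data already collected and a short text clarification. Reported cytopenia rates may look less favourable.

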#### 6.1.2.2 Hospitalizations

Hospitalizations or prolonged hospitalization for the following will not be recorded unless one of the other criteria for seriousness are met (Section [8.1.2](#)):

- Closer monitoring and/or prophylaxis of TLS during any cycle
- Closer monitoring and/or prophylaxis of IRR during any cycle

### 6.2 DATA SHARING PLANS

#### 6.2.1 Human Data Sharing Plan

##### What data will be shared?

I will share human data generated in this research for future research as follows:

Coded, linked data in an NIH-funded or approved public repository.

Coded, linked data in another public repository

Coded, linked data in BTRIS (automatic for activities in the Clinical Center)

Identified or coded, linked data with approved outside collaborators under appropriate agreements.

##### How and where will the data be shared?

Data will be shared through:

An NIH-funded or approved public repository. Insert name or names: [ClinicalTrials.gov](#), [dbGaP](#).

BTRIS (automatic for activities in the Clinical Center)

Approved outside collaborators under appropriate individual agreements.

Publication and/or public presentations.

##### When will the data be shared?

Before publication.

At the time of publication or shortly thereafter.

#### 6.2.2 Genomic Data Sharing Plan

Unlinked genomic data will be deposited in public genomic databases such as dbGaP in compliance with the NIH Genomic Data Sharing Policy.

### 6.3 RESPONSE CRITERIA

In general, response rate will be assessed according to the Lugano response criteria for FL, MCL and MZL; and the International Workshop on Chronic Lymphocytic Leukemia (iwCLL) criteria for CLL. Notable exceptions are mentioned below.

- iwCLL criteria may also be used for MCL when the disease involves peripheral blood, bone marrow or spleen without significant lymphadenopathy.
- Separate response criteria for splenic marginal zone lymphoma as proposed by Matutes et al.([121](#))
- For patients with MALT lymphoma of the ocular adnexa, an MRI based response criteria will be used in conjunction with ophthalmologic evaluation.([122](#))
- Group d'Etude des Lymphomes de l'Adult (GELA) grading system to define the histologic response of gastric MALT lymphoma will be utilized for gastric marginal zone lymphoma of MALT type.([123](#))

### 6.3.1 Response Criteria – FL, MCL and MZL

The Lugano Classification of Response will be used to assess response in subjects with FL, MZL and MCL, with the exception of CLL.

Lugano classification of response criteria with PET (Cheson et al., 2014)([124](#)):

| Response and Site                    | PET-CT Based Response  | CT-Based Response  |
|--------------------------------------|--|--|
| Complete                      | Complete metabolic response   | Complete radiologic response
All of the following:  |
| Lymph nodes and extralymphatic sites | Score 1, 2, or 3* with or without a residual mass on 5PS†  | 

• Target nodes/nodal masses must regress to <math>\leq 1.5</math> cm in LDi

• No extralymphatic sites of disease

 
NOTE: It is recognized that in Waldeyer's ring or extranodal sites with high physiologic uptake or with activation within spleen or marrow (e.g., with chemotherapy or myeloid colony-stimulating factors), uptake may be greater than normal mediastinum and/or liver. In this circumstance, complete metabolic response may be inferred if uptake at sites of initial involvement is no greater than surrounding normal tissue even if the tissue has high physiologic uptake.
 |
| Nonmeasured lesions                  | Not applicable   | Absent   |
| Organ enlargement                    | Not applicable   | Regress to normal  |
| New lesions                          | None   | None   |
| Bone marrow                          | No evidence of FDG-avid disease in marrow  | Normal by morphology; if indeterminate, IHC negative   |
| Partial                       | Partial metabolic response  | Partial remission
All of the following:   |
| Lymph nodes and extralymphatic sites | Score 4 or 5† with reduced uptake compared with baseline and residual mass(es) of any size
At interim, these findings suggest responding disease.
At end of treatment, these findings indicate residual disease. | 

• <math>\geq 50\%</math> decrease in SPD of up to 6 target measurable nodes and extranodal sites

 
When a lesion is too small to measure on CT, assign 5 mm x 5 mm as the default value; when no longer visible, 0 x 0 mm. For a node <math>> 5</math> mm x 5 mm, but smaller than normal, use actual measurement for calculation.
  |
| Nonmeasured lesions                  | Not applicable   | Absent/normal, regressed, but no increase  |
| Organ enlargement                    | Not applicable   | Spleen must have regressed by $> 50\%$ in length beyond normal   |
| New lesions                          | None   | None   |

| Response and Site                             | PET-CT Based Response   | CT-Based Response  |
|---|---|--|
| Bone marrow                                   | Residual uptake higher than uptake in normal marrow but reduced compared with baseline (diffuse uptake compatible with reactive changes from chemotherapy allowed). If there are persistent focal changes in the marrow in the context of a nodal response, consideration should be given to further evaluation with MRI or biopsy or an interval scan. | Not applicable   |
| No response or stable disease          | No metabolic response  | Stable disease  |
| Target nodes/nodal masses, extranodal lesions | Score 4 or 5 with no significant change in FDG uptake from baseline at interim or end of treatment  | <50% decrease from baseline in SPD of up to 6 dominant, measurable nodes and extranodal sites; no criteria for progressive disease are met   |
| Nonmeasured lesions                           | Not applicable  | No increase consistent with progression  |
| Organ enlargement                             | Not applicable  | No increase consistent with progression  |
| New lesions                                   | None  | None   |
| Bone marrow                                   | No change from baseline   | Not applicable   |
| Progressive disease                    | Progressive metabolic disease  | Progressive disease
Requires at least 1 of the following:   |
| Individual target nodes/nodal masses          | Score 4 or 5 with an increase in intensity of uptake from baseline; and/or   | An individual node/lesion must be abnormal with: 
 
• LDi >1.5 cm, and
 
• Increase by ≥ 50% from PPD nadir, and
 
• An increase in LDi or SDi from nadir: 
 
◦ 0.5 cm for lesions ≤2 cm
 
◦ 1.0 cm for lesions >2 cm
 
 
 
 |
| Extranodal lesions                            | New FDG-avid foci consistent with lymphoma at interim or end of treatment assessment  | 
 
• In the setting of splenomegaly, the splenic length must increase by >50% of the extent of its prior increase beyond baseline (e.g., a 15-cm spleen must increase to >16 cm). If no prior splenomegaly, must increase by at least 2 cm from baseline.
 
• New or recurrent splenomegaly
 
  |
| Nonmeasured lesions                           | None  | New or clear progression of preexisting nonmeasured lesions  |
| New lesions                                   | New FDG-avid foci consistent with lymphoma rather than another etiology (e.g., infection, inflammation). If uncertain regarding etiology of new lesions, biopsy or interval scan may be considered.   | 
 
• Regrowth of previously resolved lesions
 
• A new node >1.5 cm in any axis
 
• A new extranodal site >1.0 cm in any axis; if <1.0 cm in any axis, its presence must be unequivocal and must be attributable to lymphoma
 
• Assessable disease of any size unequivocally attributable to lymphoma
 
            |
| Bone marrow                                   | New or recurrent FDG-avid foci  | New or recurrent involvement   |

| Response and Site   | PET-CT Based Response | CT-Based Response |
|---|-----------------------|-------------------|
| 
Abbreviations: 5PS, 5-point scale; CT computed tomography; FDG, fluorodeoxyglucose; IHC, immunohistochemistry; LDi, longest transverse diameter of a lesion; MRI, magnetic resonance imaging; PET, positron emission tomography; PPD, cross product of the LDi and perpendicular diameter; SDi, shortest axis perpendicular to the LDi; SPD, sum of the product of the perpendicular diameters for multiple lesions.
 
*A score of 3 in many patients indicates a good prognosis with standard treatment, especially if at the time of an interim scan. However, in trials involving PET where de-escalation is investigated, it may be preferable to consider a score of 3 as inadequate response (to avoid under treatment). Measured dominant lesions: Up to 6 of the largest dominant nodes, nodal masses, and extranodal lesions selected to be clearly measurable in 2 diameters. Nodes should preferably be from disparate regions of the body and should include, where applicable, mediastinal and retroperitoneal areas. Non-nodal lesions include those in solid organs (e.g., liver spleen, kidneys, and lungs), GI involvement, cutaneous lesions, or those noted on palpation. Nonmeasured lesions: Any disease not selected as measured, dominant disease and truly assessable disease should be considered not measured. These sites include any nodes, nodal masses, and extranodal sites not selected as dominant or measurable or that do not meet the requirements for measurability but are still considered abnormal, as well as truly assessable disease, which is any site of suspected disease that would be difficult to follow quantitatively with measurement, including pleural effusions, ascites, bone lesions, leptomeningeal disease, abdominal masses, and other lesions that cannot be confirmed and followed by imaging. In Waldeyer's ring or in extranodal sites (e.g., GI tract, liver, bone marrow), FDG uptake may be greater than in the mediastinum with complete metabolic response but should be no higher than surrounding normal physiologic uptake (e.g., with marrow activation as a result of chemotherapy of myeloid growth factors).
 
†PET 5PS: 1, no uptake above background; 2, uptake <math>\leq</math> mediastinum; 3, uptake <math>></math> mediastinum but <math>\leq</math> liver; 4, uptake moderately <math>></math> liver; 5, uptake markedly higher than liver and/or new lesions; X, new areas of uptake unlikely to be related to lymphoma.
 |                       |                   |
|   |                       |                   |

### 6.3.2 Response Criteria – CLL

The response rate in CLL patients will be calculated based on iwCLL response criteria (Hallek et al 2018)(90):

| Complete remission (CR)  |
|--|
| Requires all of the following criteria:   |
| 

• Absolute lymphocyte count <math><4000/\text{microL}</math> (<math>4 \times 10^9/\text{L}</math>).

• No lymph nodes <math>>1.5</math> cm in diameter.

• No hepatomegaly or splenomegaly.

• No constitutional symptoms attributable to CLL.*

• Bone marrow recovery as demonstrated by ANC <math>>1500/\text{microL}</math> (<math>1.5 \times 10^9/\text{L}</math>), platelet count <math>>100,000/\text{microL}</math> (<math>100 \times 10^9/\text{L}</math>), and hemoglobin concentration <math>>11 \text{ g/dL}</math> (110 g/L) in the absence of transfusion or growth factor support.

• Bone marrow at least normocellular for age, without evidence for typical CLL lymphocytes by morphologic criteria and immunohistochemistry and without nodular lymphoid aggregates.†

 |
| CR with incomplete bone marrow recovery (CRi)  |
| Fulfills all requirements for CR except has persistent neutropenia, anemia, or thrombocytopenia thought to be unrelated to the disease and likely related to drug toxicity. These patients must have a normal bone marrow aspirate and biopsy with no evidence of clonal infiltrates.  |
| Partial remission (PR)   |
| At least two of these criteria must be documented:  |
| 

• A decrease in the peripheral absolute lymphocyte count by at least 50% from the level prior to therapy.

  |

- A reduction in previously enlarged nodes by at least 50% with no increase in the size of any single lymph node and no new enlarged lymph nodes. An increase of <25% in a lymph node <1.5 cm is not considered significant.
- A decrease in the size of the liver and/or spleen by at least 50%.

One of the following hematologic parameters must be met in addition to two of the above criteria in order to qualify for a PR:

- Platelet count  $\geq 100,000/\text{microL}$  ( $100 \times 10^9/\text{L}$ ) or at least 50% improvement over baseline (if this value was abnormally low at baseline).
- Hemoglobin concentration  $\geq 11 \text{ g/dL}$  ( $110 \text{ g/L}$ ) or 50% improvement over baseline (if this value was abnormally low at baseline) without red blood cell transfusions or erythropoietin support.

If only one parameter was abnormal before therapy, only one needs to improve to achieve PR.

